The specific monitoring plan for this study is based on the potential risk of participation and size and complexity of the planned investigation. Based on these considerations, this study will have a monitoring board comprised of [name], [name], [name], [name], and [name], the study biostatistician. The monitoring board will meet to review data after enrollment of 20 participants. All reports of a Serious Adverse Event (SAE) or an Unexpected Adverse Event will be investigated by the monitoring team and reported to Washington University HRPO according to the reporting requirements.

3.b Adverse Events

Adverse events will be tracked from the time of dose administration through post dose and at the follow up visit 3 for drug-related adverse events. All adverse events will be documented and assessed for relatedness to the study medication. The study team will monitor for adverse events on an ongoing basis. Once the team becomes aware of an adverse event, the AE will be reported according to institutional guidelines.

G Statistical Plan

G1 Sample Size Determination and Power

Sample size estimate for the proposed study is based on our team's previous pilot study with 50% of participants reporting slightly improved olfactory dysfunction at 1 month.

A power analysis was performed using Fisher's exact test in G-Power 3.1.2. Our recently completed SGB trial showed that 1 month after injection, 35% of the participants had an improvement of 15 points or more in ODOR total score. Using a clinically important difference of 25% in proportions of responders between active treatment and control group, we estimated using an exact test that a sample size of 114 subjects (38 controls

and 76 cases) will be needed to detect with 80% power at the 2-sided alpha level of 0.05.

Considering a 20% drop-out rate the total sample size to enroll is up to 140 participants.

G2 Interim Monitoring and Early Stopping

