We plan to perform an interim futility analysis. The recruitment will be halted and we will perform interim analysis when the first 40 subjects randomized and who have successfully completed treatment will have completed their 1-month post treatment assessment. Comparison of the primary endpoint between the 2 study groups will be evaluated for the interim futility analysis. Fisher's exact test will be used for the analysis given the small sample size. Conditional power (CP) with is the probability of finding statically significant results at the end of the trial, given the information obtained at interim analysis will be calculated using Mehta & Pocock CP equation. If CP<20% the result will be considered as suggestive of futility and it will serve only as a guideline that initiates more comprehensive discussion as to whether the course of the study should be modified. The data will be frozen for analysis and will be saved, so that additional analyses may be performed, or the analyses recreated, if necessary. Interim comparative data will be considered confidential and the results will be provided in a blinded fashion to research team members.

G3 Analysis Plan

Standard descriptive statistics will be used to describe distribution of baseline characteristics in each of the study groups. The effect of the intervention will be measured as the between-subject change in DisODOR.

The 95% confidence interval around this effect size will be determined to assess the precision of the observed effect and whether a clinically meaningful difference is plausible given the observed results. The DisODOR has an MCID of 15 points. A difference of at least 25% from the saline group is considered clinically meaningful. **If a greater than 25% proportion difference in responder rate is achieved in favor of the SGB group, we will offer the SGB to the placebo group at the conclusion of the study.** This will be submitted as a modification to the study.

Appropriate analyses will be performed for the secondary outcome measures.

H Data Handling and Record Keeping

H1 Confidentiality and Security

The secure REDCap database will be used to store data. Only study team members will have access to the database.

I Study Monitoring, Auditing, and Inspecting

I1 Study Monitoring Plan

The regulatory coordinator with the assistance of the study team will:

- Review of credentials, training records, and delegation of responsibility logs.
- Review of Consent Forms:

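### Cheap improvement, not an error: Boschloo's exact test would add about 0.7 to 2.2 points of power over Fisher's test, the only test the plan names for the responder endpoint

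*Combined protocol and SAP*

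**What the plan says.** G1 names the sizing method as Fisher's "exact test in G-Power 3.1.2". The effect is given as follows: "Using a clinically important difference of 25% in proportions of responders between active treatment and control group". The result is 114 evaluable participants, 38 on saline and 76 on active treatment, a number that "will be needed to detect with 80% power at the 2-sided alpha level of 0.05". G1 also cites a pilot in which 35% of participants improved by at least 15 points, and it allows for 20% drop-out with up to 140 enrolled. Randomisation is 2:1 (section 2.d). No responder rate for the saline group is given.

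G2 compares the primary endpoint between groups in the first 40 treated participants, and for that look "Fisher's exact test will be used for the analysis given the small sample size". The look leads to a conditional-power guideline (below 20% suggests futility).

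G3 describes the effect as a change in DisODOR with a 95% confidence interval, gives a 15-point threshold for the score, and treats a 25% difference in responder rate as clinically meaningful. It names no hypothesis test for the final comparison, and no other test for the responder endpoint appears in the document.

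**The concern.** Fisher's test conditions on the total number of responders. With groups of this size, few outcomes are then possible for each total, and the rejection region rarely uses the full 5%. The alpha left unused costs power and buys no validity, because an unconditional exact test also guarantees at most 5%.

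Boschloo's test takes the Fisher p-value as its statistic and raises the cut-off as far as the 5% limit allows. It therefore rejects wherever Fisher's does, and in some further tables. At stake are a few points of power for the same participants. No error-rate guarantee is at stake.

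**Working it through.** **Inputs.** From G1: 38 control, 76 active, two-sided alpha 0.05, a 25-point difference, 80% power, 20% drop-out, up to 140 enrolled. The saline rate is my assumption. It runs from 10% (the pilot's 35% read as the active rate, 35 − 25) to 35% (the pilot's rate read as the saline rate).

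**Reproducing 114.** The figure cannot be pinned down without the saline rate and the two-sided convention, but it is plausible.
- 10% vs 35%: Fisher's test in doubled-tail form (each tail at most 0.025) first reaches 80% at 37 + 74 = 111 and has 81.2% at 114. In minimum-likelihood form (summing all tables no more probable than the observed one) it first reaches 80% at 108 and has 84.1% at 114.
- 15% vs 40%: the pooled normal formula gives exactly 38 + 76 = 114, where minimum-likelihood Fisher has 78.9%.
- 35% vs 60%: 114 does not reproduce (Fisher 69.3%).

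**Method.** Enumerate all 39 × 77 tables (x responders of 38, y of 76), each with its minimum-likelihood two-sided Fisher p-value P(x, y).
- Size at common rate p: sum of b(x; 38, p) × b(y; 76, p) over tables with P ≤ c.
- Power: the same sum with rate p for saline and p + 0.25 for active.
- Fisher: c = 0.05. Boschloo: the largest c whose size, maximised over p, is at most 0.05. This gives c = 0.0592.

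Example: 7/38 (18.4%) vs 28/76 (36.8%) has Fisher p = 0.0537. Fisher's test does not reject; Boschloo's does, since 0.0537 < 0.0592.

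**True size at 76 vs 38.**

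| Common rate | Fisher | Boschloo |
|---|---|---|
| 10% | 3.0% | 4.4% |
| 20% | 3.7% | 4.5% |
| 30% | 3.8% | 4.8% |
| 40% | 4.2% | 4.5% |
| 50% | 4.3% | 4.5% |
| Maximum | 4.31% | 4.87% |

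Every table that Fisher rejects is also rejected by Boschloo.

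**Power at 76 vs 38, 25-point difference.** Gains are differences of the rounded powers.

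| Saline vs active | Fisher | Boschloo | Gain (points) |
|---|---|---|---|
| 10% vs 35% | 84.1% | 86.1% | 2.0 |
| 15% vs 40% | 78.9% | 81.1% | 2.2 |
| 20% vs 45% | 75.8% | 77.3% | 1.5 |
| 25% vs 50% | 73.9% | 74.6% | 0.7 |
| 30% vs 55% | 71.4% | 72.4% | 1.0 |
| 35% vs 60% | 69.3% | 70.0% | 0.7 |

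**After drop-out.** 140 × 0.8 = 112, about 75 vs 37 at 2:1. Over the same saline rates the gain there runs from about 0.1 (69.4 to 69.5% at 35%) to 4.8 points (71.5 to 76.3% at 20%). With one active participant fewer (74 vs 37) it runs from about 0.1 to 2.3 points. The gain depends on the exact split of completers.

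**The case against.** The strongest reply is that nothing in the plan is wrong. Fisher's test keeps the error rate below 5%, it is a standard choice, and G1 used it to size the trial, so its conservatism is already paid for in the 114. All of that stands, and it is why this is an optional improvement.

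Four stronger readings are tempting, and the documents do not support them.
- *That the plan prescribes Fisher's test for the final analysis.* G3 names no test. Fisher's use there is inferred from G1 and G2.
- *That the futility look is harmed.* That look feeds a guideline and spends no alpha. The 3.0 to 4.3% range does not describe it either: at about 27 vs 13 the size is 1.7 to 4.2% for common rates of 10 to 50%.
- *That nearly 5 points of power are lost after drop-out.* The 4.8-point figure belongs to one split and one saline rate. Completer numbers cannot be known in advance, so no single post-dropout gain should be quoted.
- *That the loss is 5 to 8 points.* If Fisher's test were run in doubled-tail form and replaced by Boschloo's at 0.025 per side, the gain would be 5.2 to 7.6 points. The documents do not say which two-sided form is meant, so the smaller figures are the ones to use.

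**Conclusion.** The point holds as an efficiency improvement. At the planned 76 vs 38, Fisher's test runs at about 3.0 to 4.3% for common rates of 10 to 50%. Boschloo's test adds about 0.7 to 2.2 points of power for saline rates of 10 to 35% and a 25-point difference. This assumes the minimum-likelihood two-sided form, an unadjusted comparison, and full completion of the 114.

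A reader might infer that the choice of test explains any shortfall against 80% power. It does not. Over the saline rates shown, Fisher's power falls from 84.1% to 69.3%, a span of 14.8 points against at most 2.2 from the test. Changing the test lifts power across 80% in only one row (15% vs 40%, 78.9 to 81.1%). The unstated saline rate matters far more, and Boschloo's test does not repair it.

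**What to change.** - In G3, before unblinding, name Boschloo's exact unconditional test at two-sided 0.05 for any unadjusted final responder comparison. State the two-sided convention and the software, since implementations differ.
- Report the difference in responder proportions with an exact unconditional 95% confidence interval.
- In G1, quote the power at 76 vs 38 for that test and state the saline rate assumed, preferably over a range.
- Leave the G2 futility look unchanged.

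The cost is a few sentences; standard software computes the test, and no participants are added. The downside is that clinical readers know the test less well, so the Fisher p-value may be reported beside it, with Boschloo's named in advance as the one that decides.

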Recently, our study team completed a prospective, pilot single-arm trial of 20 participants with persistent COVID-19-associated OD who underwent bilateral stellate ganglion blocks and were followed for 1 month post-procedure. At 1-month, 10 (50%) participants experienced at least slight subjective improvement in their OD, 11 (55%) attained a clinically meaningful improvement in smell identification using the UPSIT, and 7 (35%) achieved a clinically meaningful improvement in olfactory-specific QOL. Therefore, we propose a double-blinded, placebo-controlled randomized clinical trial assessing the efficacy of a stellate ganglion block versus saline injection in a total of 140 participants with persistent COVID-19-associated parosmia.

C Study Objectives

C1 Primary Aim

1. To determine the efficacy of a SGB in improving parosmia-related quality of life compared to saline injection

C2 Secondary Aim

1. To determine the efficacy of a SGB in improving self-reported parosmia compared to saline injection
2. To determine the safety and tolerability of a SGB
3. To determine if subjects who catastrophize their parosmia smell loss are more likely to respond to SGB
4. To determine if subjects who screen positive for anxiety/depression are more likely to respond to SGB
5. Explore if there is variation of SGB effect dependent on injection laterality (right versus left SGB)

C3 Rationale for the Selection of Outcome Measures

Parosmia Olfactory Dysfunction Outcomes Rating (DisODOR). The DisODOR is a disease-specific questionnaire that assesses for physical problems, functional limitations, and emotional consequences of parosmia secondary to any etiology. The instrument contains 29 total items with each scored on a 5-point Likert scale from 0 to 4.

Clinical Global Impression - Severity Scale (CGI-S). The baseline severity of parosmia will be measured with the *CGI-S* scale. The *CGI-S* scale measures disease severity in clinical condition based on a 5-point Likert scale.

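### G1 and G2 name only Fisher's exact test on responders, while G3 measures change in DisODOR and names no final test: the primary comparison should be fixed on the full score, and conditional power computed from that same statistic.

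*Combined protocol and SAP*

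**What the plan says.** The primary aim (C1) is improvement in parosmia-related quality of life, measured by DisODOR. Section C3 describes the scale: "The instrument contains 29 total items with each scored on a 5-point Likert scale from 0 to 4". The total therefore runs from 0 to 29 × 4 = 116. The schedule in F2 collects it at baseline, 1 month and 3 months.

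Three places bear on how the arms are compared.

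- **G1 (sample size).** "A power analysis was performed using Fisher's exact test in G-Power 3.1.2". The pilot input is that "35% of the participants had an improvement of 15 points or more in ODOR total score". The effect is set as follows: "Using a clinically important difference of 25% in proportions of responders between active treatment and control group, we estimated using an exact test", and the requirement is 38 controls "and 76 cases) will be needed to detect with 80% power at the 2-sided alpha level of 0.05". The control rate is not stated.
- **G2 (interim).** The primary endpoint is compared when 40 treated participants reach 1 month: "Fisher's exact test will be used for the analysis given the small sample size". Conditional power below 20% suggests futility, but only as a prompt for discussion.
- **G3 (analysis).** The effect is the change in DisODOR with a 95% confidence interval. "The DisODOR has an MCID of 15 points", and a 25% difference from saline counts as clinically meaningful. A responder difference above 25% also triggers an offer of the block to saline participants. No hypothesis test and no timepoint are named.

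No section defines the primary endpoint as DisODOR improvement of at least 15 points, yes or no. That cut is inferred from G1's pilot figure (which is on the ODOR) and G3's MCID. The only written definition of a responder, in C3, is on the CGI-I.

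**The concern.** Fisher's exact test needs a yes/no outcome, so G1 and G2 imply that a graded score is split at 15 points. A change of 14 then counts the same as no change, and a change of 15 the same as 60. G3 reads more naturally as a comparison on the full score. The two do not fit together, and either resolution leaves a problem:

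- If the final test is on responders, the trial gives up information it has already collected, with only 38 saline participants to spare.
- If the final test is on change in DisODOR, the interim conditional power is worked out for a different statistic from the one that decides the trial.

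At the interim, about 13 participants will have had saline. With a 10% saline rate, the chance of two or fewer responders among 13 is 87%, so a responder-based conditional power rests on very few events.

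**Working it through.** **Inputs.** From G1: 38 and 76 analysed, two-sided 0.05, 80% power, pilot rate 35%, difference 25 points. From G2: 40 participants, conditional power below 20%. Assumed: 13 saline and 27 active at the interim (2:1 allocation); control rate 35% − 25% = 10%. The documents give no SD or distribution for DisODOR change, so each figure for the full score depends on a stated model.

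**Step 1: reproduce 114.** Exact enumeration of Fisher's test at 38/76 with 10% vs 35% gives 84.1% power (minimum-likelihood two-sided p) or 81.2% (doubled one-sided p). With the doubled p, 80% is first reached at 111 (37/74). So 114 is consistent with 10% vs 35%. Reading the rates as 35% vs 60% gives only 69.3% (or 64.0%), so 10% vs 35% is taken as the design pair.

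**Step 2: final power under a normal shift with equal SD.** Standardised shift d = Φ⁻¹(p_active) − Φ⁻¹(p_saline). For the design pair, d = −0.385 + 1.282 = 0.896. Noncentrality = d × √(38 × 76/114) = 0.896 × 5.033 = 4.51, on 112 df.

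| Active vs saline | d | Fisher | Uncorrected chi-square | t-test on change | t-test minus Fisher |
|---|---|---|---|---|---|
| 35% vs 10% | 0.896 | 84.1% | 86.5% | 99.4% | 15.3 |
| 50% vs 25% | 0.674 | 73.9% | 74.9% | 92.0% | 18.1 |
| 60% vs 35% | 0.639 | 69.3% | 73.4% | 89.0% | 19.7 |

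The chi-square column uses the same cut, so chi-square minus Fisher (1 to 4 points) is the cost of Fisher's conservatism and not of the cut.

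**Step 3: benefit confined to a subgroup.** Take saline mean change 0 and SD 15/1.282 = 11.7, so that 10% pass the cut. A fraction f of active participants gains D points, with f chosen to keep 35% above the cut (100,000 simulated trials per row). The flag column is the share with conditional power below 20% on the equal-variance t statistic, using the rule in step 4.

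| D | f | Equal-variance t | Welch t | Interim flag, full score |
|---|---|---|---|---|
| 12 | 84% | 98.5% | 98.6% | 4.5% |
| 15 | 63% | 95.4% | 96.3% | 7.8% |
| 20 | 44% | 89.4% | 92.3% | 12.0% |
| 25 | 36% | 85.9% | 90.5% | 13.9% |
| 30 | 31% | 85.8% | 91.4% | 13.5% |

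Against Fisher's 84.1%, the smallest margin is about 2 points (equal variance) or 6 points (Welch).

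**Step 4: interim flags.** Current-trend conditional power is CP = 1 − Φ((1.96 − z/√t)/√(1 − t)), with t = 40/114 = 0.351. CP < 0.20 means z < √t × (1.96 − 0.842 × √(1 − t)) = 0.592 × 1.282 = 0.76.

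- Full score, normal shift, design pair: expected z = 0.896/√(1/13 + 1/27) = 0.896/0.3376 = 2.65, and Φ(0.76 − 2.65) ≈ 2.9%; with the t distribution, 3.0%.
- Responders, pooled z, design pair, by enumeration: 14.0%. The ratio is 14.0/3.0, or about 4.6.
- At 60% vs 35%: 20.0% on responders vs 12.9% on the full score, about 1.6-fold.
- Under subgroup benefit: about 14% on responders vs the last column of step 3, so from about threefold to no difference.

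G2 does not say how Fisher's test feeds the conditional power equation. For the responder flag at the design pair, an unpooled z gives 11.4%, a z from Fisher's two-sided p gives 20.5%, and one from its one-sided p gives 24.3%.

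**The case against.** The strongest reply is that G3 is the analysis section and already describes change in DisODOR with a confidence interval. G1's Fisher test is a sizing calculation, and G2's is justified there by the small interim sample. That stands. A reader might infer that the plan commits the final analysis to the 15-point cut, and so loses about 15 points of power and multiplies wrong futility flags fivefold. The documents do not support this: no final test is named, the cut is inferred, and those figures hold only for one distribution that the documents do not give.

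The subgroup case also has weight. The pilot's results (50% with any subjective improvement, 35% with a meaningful quality-of-life gain) are compatible with benefit in some participants only. With subgroup gains of 25 to 30 points, the equal-variance t-test (about 86%) is no better than an uncorrected chi-square on the cut (86.5%), so its 2-point margin over Fisher owes nothing to avoiding the cut.

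Fisher's test meets the stated 80% at the design pair, so G1's calculation is not wrong. A responder endpoint also matches the plan's own idea of clinical meaning, and a test of means asks a different question. With SD 11.7, a mean difference of about 1.98 × 11.7 × √(1/38 + 1/76) = 4.6 points would be significant, well below the MCID of 15.

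Finally, a futility flag opens a discussion and does not by itself stop the trial. None of this removes the mismatch between G2 and G3 or the missing final test.

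**Conclusion.** The concern holds in limited form. The plan names Fisher's test on responders for sizing and for the interim, describes the final effect on a different scale, and leaves the final test open. Comparing the full score had higher power than Fisher's test in every scenario examined, but the size of the gain is uncertain.

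- **Final power, design pair (35% vs an inferred 10%):** a gain of about 2 to 15 points, depending on whether benefit is a general shift or confined to a subgroup. It is about 18 to 20 points at 50% vs 25% or 60% vs 35% under a normal shift. Of these gains, 1 to 4 points reflect Fisher's conservatism.
- **Wrong futility flags (pooled z):** about 14% on responders against 3% on the full score under a normal shift, but between 4% and 15% on the full score under subgroup benefit, and 20% vs 13% at 60% vs 35%. The advantage runs from about fivefold to none.

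These figures rest on the inferred 10% saline rate, the inferred 15-point cut, a 27/13 interim split and the stated distributions. This is a worthwhile, inexpensive improvement, and not a demonstration that the trial is underpowered.

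**What to change.** Before any unblinded comparison:

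1. **G3:** name the between-arm difference in mean DisODOR change, at a stated timepoint, as the primary test, by linear model or Welch t-test, with its 95% confidence interval. Welch held its power better in the subgroup scenarios.
2. **G2:** compute conditional power from that same statistic, in place of the Fisher comparison.
3. **Supporting analysis:** keep the difference in the proportion improving by at least 15 points, with its confidence interval, as the key supporting result. The MCID interpretation and the 25% responder rule then stay as written.
4. **G1:** leave the sample size at 114. The power gain depends on a distribution that has not been documented, so it is no ground for a smaller trial.

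The cost is wording only: no new data, visits or participants. The downside is that the primary p-value will refer to a mean difference that can be significant below the 15-point MCID, so clinical meaning must be read from the responder analysis. If only a subgroup benefits, the gain in power is small.

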Olfaction Catastrophizing Scale (OCS). The pain catastrophizing scale (PCS) was developed to measure the negative mental response to actual or anticipated pain. The *OCS* was derived from the validated PCS to similarly measure the negative mental response to smell dysfunctionloss. Multiple thoughts/feelings will be assessed on a 5-point likert scale with a maximum score of 52. At each visit, subjects will be asked to complete the *OCS*.

Hospital Anxiety and Depression Scale (HADS). The *HADS* was developed for screen for anxiety and depression in the general population. It consists of 7 questions for anxiety and 7 questions for depression each ranked on a 4-point Likert Scale. A score of 0-7 is considered normal, 8-10 is borderline abnormal anxiety or depression, and a score of 11-21 corresponds with screening positive for anxiety or depression. Subjects will be screened for anxiety and depression at eachtheir initial visit.

Pre-Intervention Expectations. A significant number of social media and news stories have discussed anecdotal success of stellate ganglion blocks for COVID-19-induced olfactory dysfunction. As a result, we propose that participants may have a distorted pre-operative expectation that may affect their subjective rating of improvement in olfaction. Therefore, participants will be asked at baseline, "How confident are you that the stellate ganglion block will improve your smell loss or smell distortion?" Possible answer choices: Not at all, Slightly confident, Somewhat confident, Very confident, Extremely confident.

Patient Satisfaction with Treatment. Participants will be asked at the 1-month virtual visit, "Overall, how satisfied were you with the stellate ganglion block treatment for your parosmia?" Possible answer choices: 1) Completely dissatisfied, 2) Mostly dissatisfied, 3) Somewhat dissatisfied, 4) Neither satisfied or dissatisfied, 5) Somewhat satisfied, 6) Mostly satisfied, 7) Completely satisfied. Patients will also be asked at the final visit, "Would you recommend this treatment to a family member or close friend who also suffers from chronic smell loss due to COVID-19?" Possible answer choices: 1) Yes, 2) No.

Assessment of the Blind. Immediately after the initial injection, participants will be asked, "Which intervention do you think you received?" Answer choices: 1) Mepivacaine (active medication) 2) Saline (placebo).

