The study will be a single center, double-blinded, placebo-controlled randomized clinical trial conducted at Washington University School of Medicine.

E2 Subject Selection

2.a Inclusion Criteria

- 1) Adults age 18 to 70
- 2) Diagnosis of COVID at least 6 months prior to study enrollment with self-reported parosmia
- 3) Ability to read, write, and understand English
- 4) Score of at least 40 on DiSODOR during screening and at least 25 during Visit 1

2.a Exclusion Criteria

- 1) History of smell loss or change prior to COVID-19 infection
- 2) History of conditions known to impact olfactory function:
 - a. Chronic rhinosinusitis
 - i. If individual notes a history of chronic rhinosinusitis or prior endoscopic sinus surgery, they may be eligible if they can a note from their otolaryngology (ENT) physician stating the following:
 1. Patient's chronic rhinosinusitis is controlled
 2. There are no polyps/masses/scarring of the olfactory cleft
 3. The otolaryngologist feels that the patient's parosmia is secondary to COVID-19
 - b. History of prior sinonasal or skull base surgery
 - c. Neurodegenerative disorders (Parkinson's disease, Huntington's disease, Amyotrophic lateral sclerosis, Lewy body dementia, frontotemporal dementia)
- 3) Currently using concomitant therapies specifically for the treatment of olfactory dysfunction
- 4) Inability to tolerate a needle injection into the neck
- 5) History of coexisting conditions that make SGB contraindicated:
 - a. Unilateral vocal cord paralysis
 - b. Severe COPD (FEV1 between 30-50% of predicted)
 - c. Recent myocardial infarction within the last year

- d. Glaucoma
- e. Cardiac conduction block of any degree
- 6) Currently taking blood thinners or antiplatelet agents, including
> 81mg aspirin
- 7) Allergy to local anesthetic
- 8) Inability to extend the neck for any reason (e.g., severe arthritis)
- 9) History of prior stellate ganglion block

2.b Ethical Considerations

Patients will be informed in the informed consent process that they may or may not personally benefit from the study and that the data obtained from the study will be used to inform the future care patients with chronic COVID-19-induced olfactory dysfunction. There will be phone assistance available 24/7 during the study period to report any possible adverse reactions. There are no financial conflicts of interest.

2.c Subject Recruitment Plans and Consent Process

Study recruitment strategies include:

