Placebo Injection. The placebo sham injection will be performed in an identical fashion as the stellate ganglion block by [name] with the exception of using 6-8 mL of 0.9% saline injection instead of mepivacaine. A Horner syndrome is not expected after placebo injection, but its presence has been noted in prior studies with sham SGBs.

F Study Procedures

F1 Screening for Eligibility

To determine potential eligibility for the study, the research team will query the medical record and our team's contact database of COVID-19-induced olfactory dysfunction patients based on the inclusion/exclusion criteria. For those meeting the selection criteria, we will access name, telephone number, age, sex, and date/time of any upcoming clinic visits. For interested and potentially eligible individuals, including those contacting the study team, eligibility will be determined based on the inclusion/exclusion criteria and completion of the DisODOR questionnaire. If they have been treated at the medical center for COVID, their medical record will be accessed.

F2 Schedule of Measurements

The first visit will be completed at the Clinical and Translational Research Unit (CTRU). The second and third visits will be completed virtually.

Role of the CTRU: Nursing staff will be needed for assistance in completion of the SGB. Additionally, all subjects will have vital signs monitored with serial blood pressures, respiratory rate, heart rate, and pulse oximetry within the CTRU for a minimum of 10 minutes after completion of the block to ensure patient stability prior to discharge. Additional monitoring will be provided as needed based on patient response to the procedure. Participants will be discharged once stability is determined and instructed to continue wearing an eye patch for an additional 2 hours. It will be ensured that they have someone to drive them home prior to discharge.

Visit 1

At the initial visit, demographic information, including age, sex, race, and length of time of parosmia will be collected from each enrolled patient. Prior to undergoing the first SGB, participants will complete the Parosmia trigger question, DisODOR, UPSIT, CGI-S for Parosmia, OCS, HADS, and Pre-Intervention Expectations Questionnaire. The assessment of the blind will occur just prior to discharge from the first visit.

Visit 2

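### G3 measures the effect as raw change in DisODOR without adjusting for the Visit 1 score, so its confidence interval is wider than it need be

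*Combined protocol and SAP*

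**What the plan says.** G3 defines the effect measure: "The effect of the intervention will be measured as the between-subject change in DisODOR". It adds a 95% confidence interval, to be used to judge precision and whether a clinically meaningful difference is plausible. It names no model, final test or covariate.

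The baseline score is available for everyone. F2 (Visit 1) says "Prior to undergoing the first SGB, participants will complete the Parosmia trigger question, DisODOR, UPSIT", and the schedule of events repeats DisODOR at 1 and 3 months. Entry limits the starting score: "Score of at least 40 on DiSODOR during screening and at least 25 during Visit 1" (E2). With 29 items scored 0 to 4 (C3), the maximum is 116.

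The only between-arm test named is Fisher's exact test. In G1 it is used for sizing: "A power analysis was performed using Fisher's exact test in G-Power 3.1.2". In G2 it is used for the interim futility look. The sizing endpoint is a responder proportion: "35% of the participants had an improvement of 15 points or more in ODOR total score" in the pilot at 1 month, and "Using a clinically important difference of 25% in proportions of responders between active treatment and control group". G3 gives the matching threshold: "The DisODOR has an MCID of 15 points".

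C3 also records baseline expectation, because "participants may have a distorted pre-operative expectation that may affect their subjective rating of improvement in olfaction". G3 does not mention it.

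**The concern.** Subtracting the baseline is one particular adjustment: it assumes that each extra point at baseline carries through as a full point at follow-up. On a questionnaire with measurement error, in participants selected for high scores, the expected slope is below 1. The change score then over-corrects. Two things follow. The standard error of the treatment difference is larger than under a model that estimates the slope. And if the arms differ by chance at baseline, part of that difference remains in the estimate.

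Both bear on what G3 does with its interval. A wider interval makes it harder to say whether a meaningful difference is plausible or excluded, and the saline arm is planned at only 38 evaluable participants. The information needed to narrow it is already being collected.

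**Working it through.** **Inputs from the documents:** 76 active and 38 saline evaluable, two-sided alpha 0.05, 80% power, responder threshold 15 points, pilot responder rate 35%, difference 25 points (G1, G3); entry limits 40 at screening and 25 at Visit 1 (E2).

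**Assumptions (not in the documents):** control rate 10% (35 − 25); baseline mean 60 and SD 20 before selection; equal SDs at both times; r from 0.3 to 0.9; screening/Visit 1 correlation 0.85.

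**1. The plan's own figure.** Exact enumeration of Fisher's test at 10% vs 35% and 2:1 allocation, with 0.025 in each tail, reaches 80.0% power at N = 111 and 81.2% at N = 114. With the usual two-sided p-value, power at 114 is 84.1%. The stated 114 is therefore reproduced. The true size of the latter test at a common 10% rate is 3.0%.

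**2. Precision.** With SD σ at both times, the change score has variance 2σ²(1 − r) and the ANCOVA residual σ²(1 − r²). The ratio is (1 + r)/2. Entry limits narrow the baseline spread, which brings the ratio nearer to 1. If v is the baseline variance after selection divided by σ², the ratio is (1 + r)/[(1 + r) + (1 − r)v]. Under the assumptions the selected SD is about 16.6, so v = (16.6/20)² = 0.689.

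| r | ratio, no entry limits | ratio, entry limits | equivalent extra participants | interval narrower by |
|---|---|---|---|---|
| 0.3 | 0.65 | 1.3/1.782 = 0.729 | 37% | 15% |
| 0.5 | 0.75 | 1.5/1.845 = 0.813 | 23% | 10% |
| 0.7 | 0.85 | 1.7/1.907 = 0.892 | 12% | 6% |
| 0.8 | 0.90 | 1.8/1.938 = 0.929 | 8% | 4% |
| 0.9 | 0.95 | 1.9/1.969 = 0.965 | 4% | 2% |

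Extra participants are 1/ratio − 1; narrowing is 1 − √ratio. A screening/Visit 1 correlation of 0.70 or 0.95 moves these ratios by no more than 0.02.

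**3. Chance imbalance.** The standard error of the baseline difference is √(1/38 + 1/76) = 0.20 SD. The change score retains (1 − r) of it: a one-standard-error imbalance shifts the estimate by 0.20 × 0.2 = 0.04 SD at r = 0.8 and 0.20 × 0.5 = 0.10 SD at r = 0.5. At an SD of 16.6 that is about 0.7 to 1.6 points.

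**4. Power on continuous change.** Responder rates of 10% and 35% imply a shift of z(0.35) − z(0.10) = −0.385 + 1.282 = 0.896 SD of change, taking change as normal. The noncentrality is 0.896 × √(38 × 76/114) = 4.51, and power is 99.4%. ANCOVA gives 99.7% to 99.9% for r from 0.8 to 0.5, a gain under 1 point.

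**5. Power on the 15-point responder.** Simulation at 76/38, 35% vs 10%, where Fisher has about 84%:

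| method | r | without baseline | with baseline | gain from baseline |
|---|---|---|---|---|
| risk difference, entry limits applied | 0.3 / 0.5 / 0.7 | 86.4–86.9% | 91.3 / 90.2 / 88.4% | about 4.5 / 3.5 / 1.5–2 points |
| logistic likelihood ratio, no entry limits | 0.5 / 0.6 / 0.7 / 0.8 | 88.0 / 88.1 / 88.1 / 88.7% | 92.2 / 91.3 / 90.9 / 90.2% | 4.2 / 3.2 / 2.8 / 1.5 points |

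A further run with entry limits gave 1 to 3 points. Baseline adjustment itself is thus worth about 1 to 5 points.

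**6. Sparse data.** Expected saline responders at 10% are 38 × 0.10 = 3.8, and the chance of none is 0.9^38 = 1.8%. Null error depended on the method: 4.2–5.0% for one standardised risk difference, 5.5–5.8% for the adjusted likelihood-ratio test, and 6.6–7.7% for a simple large-sample standard error.

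**The case against.** A reader might infer that the plan ignores baseline and thereby gives up 4 to 7 points of power at its own design effect. The documents do not support that.

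- Baseline is not ignored. Change subtracts it, and the 15-point responder is defined from it.
- The 4 to 7 points are the whole distance from Fisher's test to a baseline-adjusted test on the responder endpoint. Part of that comes from leaving a conservative exact test. On continuous change, the measure G3 names, less than 1 point is available.
- G3 does not commit to an unadjusted final test. Fisher's test belongs to the sizing and to the 40-subject interim, where small numbers are the stated reason. For the final analysis the plan is silent.
- Chance imbalance does not bias a randomised comparison. Only (1 − r) of it remains, and the interval already reflects that noise.
- All sizes depend on an SD, an r and a control rate that the documents do not give. At r = 0.9 almost nothing is gained.
- Recording expectation does not oblige the analysis to adjust for it.

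All of this stands, and it limits the size of the point. It does not remove it: no text in the plan would lead to baseline adjustment, and for any r below 1 under these assumptions the ANCOVA interval is narrower. Silence on the final model also leaves the choice between adjusted and unadjusted results open until after the data are seen.

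**Conclusion.** The point holds as a matter of precision and pre-specification. Raw change in DisODOR is a less efficient measure than ANCOVA on the Visit 1 score, by about 27% of the variance at r = 0.3 and about 3% at r = 0.9, under an assumed baseline mean of 60, SD 20 and the protocol's entry limits. It is not a threat to validity. Nor is it a material loss of power on continuous change at the design effect, where power is about 99%; the benefit there is a narrower interval. On the responder endpoint the contribution of baseline is about 1 to 5 points at an assumed 10% control rate, and any further gain comes from not using Fisher's test. The change is worth making because it is free, not because the trial fails without it.

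**What to change.** In G3, state that the between-arm difference in DisODOR at the 1-month visit will be estimated by ANCOVA with the Visit 1 DisODOR score as covariate, and reported with its 95% confidence interval. One month is the time point used for sizing and for the interim. Analyse 3 months the same way.

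If the responder difference is also adjusted for baseline, name an interval that is valid in small samples, for example bootstrap or permutation, because only about 4 saline responders are expected at a 10% rate. Keep the raw responder percentages as the input to the 25% responder-rate rule in G3. Adding baseline expectation as a covariate is optional.

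The cost is a paragraph of SAP wording, with no new data, visit or participant. It should be fixed before anyone sees comparative data. Whether change or the responder proportion is the primary measure (G3 against G1) is a separate matter that this wording does not settle.
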